9.4 Radiology Imaging Studies

Images of all radiologic assessments at baseline, on study, and at treatment discontinuation with corresponding imaging reports for non-DFCI patients need to be placed on a CD and sent to the DFCI for eventual central review of exploratory imaging response assessment by irRC. Images and reports should be sent on all patients once they discontinue study treatment. Please ensure that patient data is de-identified and patient study ID is referenced on all materials as detailed in the lab manual. Reference the Laboratory Manual for additional information.

9.5 Storage of Biospecimens

Samples will be processed for correlative studies and remaining specimens will be stored for future use to include assessment of biological and molecular predictive and prognostic biomarkers.

9.6 Confidentiality of Biospecimens

Samples that are collected will be identified by a subject's study number assigned at the time

of registration to the trial. Any material issued to collaborating researchers will be anonymized and only identified by the subject's study number.

10. CRITERIA FOR DISEASE EVALUATION

Subjects should be re-evaluated for response every 2 cycles. Response and progression will be evaluated in this study using the new international criteria proposed by the RECIST guideline (version 1.1).³³ Changes in the largest diameter (unidimensional measurement) of the tumor lesions and the shortest diameter in the case of malignant lymph nodes are used in the RECIST criteria.

10.1 Definitions

Evaluable for Target Disease response. Only those subjects who have measurable disease present at baseline, have received at least one cycle of therapy, and have had their disease re-evaluated will be considered evaluable for target disease response. These subjects will have their response classified according to the definitions stated below. (Note: Subjects who exhibit objective disease progression prior to the end of cycle 1 will also be considered evaluable.)

Evaluable Non-Target Disease Response. Subjects who have lesions present at baseline that are evaluable but do not meet the definitions of measurable disease, have received at least one cycle of therapy, and have had their disease re-evaluated will be considered evaluable for non-target disease. The response assessment is based on the presence, absence, or unequivocal progression of the lesions.

10.2 Disease Parameters

Measurable disease. Measurable lesions are defined as those that can be accurately measured in at least one dimension (longest diameter to be recorded) as ≥ 20 mm by chest x-ray or ≥ 10 mm with CT scan, MRI, or calipers by clinical exam. All tumor measurements must be recorded in millimeters (or decimal fractions of centimeters). **NOTE:** Tumor lesions that are situated in a previously irradiated area are not considered measurable.

Malignant lymph nodes. To be considered pathologically enlarged and measurable, a lymph node must be ≥ 15 mm in short axis when assessed by CT scan (CT scan slice thickness recommended to be no greater than 5 mm). At baseline and in follow-up, only the short axis will be measured and followed.

Non-measurable disease. All other lesions (or sites of disease), including small lesions (longest diameter < 10 mm or pathological lymph nodes with ≥ 10 to < 15 mm short axis), are considered non-measurable disease. Leptomeningeal disease, ascites, pleural/pericardial effusions, lymphangitis cutis/pulmonitis, inflammatory breast disease, abdominal masses (not followed by CT or MRI), and cystic lesions are all considered non-measurable.

Note: Cystic lesions that meet the criteria for radiographically defined simple cysts should not be considered as malignant lesions (neither measurable nor non-measurable) since they are, by definition, simple cysts.

‘Cystic lesions’ thought to represent cystic metastases can be considered as measurable lesions, if they meet the definition of measurability described above. However, if non-cystic lesions are present in the same participant, these are preferred for selection as target lesions.

Target lesions. All measurable lesions up to a maximum of 2 lesions per organ and 5 lesions in total, representative of all involved organs, should be identified as **target lesions** and recorded and measured at baseline. Target lesions should be selected on the basis of their size (lesions with the longest diameter), be representative of all involved organs, but in addition should be those that lend themselves to reproducible repeated measurements. It may be the case that, on occasion, the largest lesion does not lend itself to reproducible measurement in which circumstance the next largest lesion which can be measured reproducibly should be selected. A sum of the diameters (longest for non-nodal lesions, short axis for nodal lesions) for all target lesions will be calculated and reported as the baseline sum diameters. If lymph nodes are to be included in the sum, then only the short axis is added into the sum. The baseline sum diameters will be used as reference to further characterize any objective tumor regression in the measurable dimension of the disease.

Non-target lesions. All other lesions (or sites of disease) including any measurable lesions over and above the 5 target lesions should be identified as **non-target lesions** and should also be recorded at baseline. Measurements of these lesions are not required, but the presence, absence, or in rare cases unequivocal progression of each should be noted throughout follow up.

Methods for Evaluation of Disease

All measurements should be taken and recorded in metric notation using a ruler, calipers, or a digital measurement tool. All baseline evaluations should be performed as closely as possible to the beginning of treatment and never more than 4 weeks before the beginning of the treatment.

When possible, the same method of assessment and the same technique should be used to characterize each identified and reported lesion at baseline and during follow-up. Imaging-based evaluation is preferred to evaluation by clinical examination unless the lesion(s) being followed cannot be imaged but are assessable by clinical exam.

Clinical lesions. Clinical lesions will only be considered measurable when they are superficial (*e.g.*, skin nodules and palpable lymph nodes) and ≥ 10 mm in diameter as assessed using calipers (*e.g.*, skin nodules). In the case of skin lesions, documentation by color photography, including a ruler to estimate the size of the lesion, is recommended.

Conventional CT and MRI. This guideline has defined measurability of lesions on CT scan based on the assumption that CT thickness is 5mm or less. If CT scans have slice thickness greater than 5 mm, the minimum size of a measurable lesion should be twice the slice thickness. MRI is also acceptable in certain situations (*e.g.* for body scans).

Use of MRI remains a complex issue. MRI has excellent contrast, spatial, and temporal

resolution; however, there are many image acquisition variables involved in MRI, which greatly impact image quality, lesion conspicuity, and measurement. Furthermore, the availability of MRI is variable globally. As with CT, if an MRI is performed, the technical specifications of the scanning sequences used should be optimized for the evaluation of the type and site of disease.

Furthermore, as with CT, the modality used at follow-up should be the same as was used at baseline and the lesions should be measured/assessed on the same pulse sequence. It is beyond the scope of the RECIST guidelines to prescribe specific MRI pulse sequence parameters for all scanners, body parts, and diseases. Ideally, the same type of scanner should be used and the image acquisition protocol should be followed as closely as possible to prior scans. Body scans should be performed with breath-hold scanning techniques, if possible.

10.3 Response Criteria

10.3.1 Evaluation of Target Lesions

Complete Response (CR): Disappearance of all target lesions. Any pathological lymph nodes (whether target or non-target) must have reduction in short axis to <10 mm.

Partial Response (PR): At least a 30% decrease in the sum of the diameters of target lesions, taking as reference the baseline sum diameters.

Progressive Disease (PD): At least a 20% increase in the sum of the diameters of target lesions, taking as reference the smallest sum on study (this includes the baseline sum if that is the smallest on study). In addition to the relative increase of 20%, the sum must also demonstrate an absolute increase of at least 5 mm. (Note: the appearance of one or more new lesions is also considered progression). For subjects who demonstrate PD at the first on-treatment imaging assessment, subjects will be allowed to remain on study until confirmatory imaging at the next imaging assessment at the discretion of the treating investigator if it appears that the subjects is clinically benefiting from treatment.

Stable Disease (SD): Neither sufficient shrinkage to qualify for PR nor sufficient increase to qualify for PD, taking as reference the smallest sum diameters while on study.

If a target lesion is biopsied at screening, this lesion must be followed as non-target lesion after the biopsy unless it is the patient's only target lesion. If there is only one target lesion, it should be followed as a target lesion regardless.

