Subjects in Arm B will receive ipilimumab every three weeks x 2 doses in addition to nivolumab. Treatment with nivolumab alone every 4 weeks will begin 5 weeks \pm 3 days after the last dose of nivolumab + ipilimumab. Subjects will be followed with serial imaging assessments every 8 weeks (except the first imaging assessment which will take place at 12 weeks since ipilimumab addition). If PD persists or develops, all treatments will be discontinued. If PR/CR/SD is observed subjects will continue nivolumab.

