6.7 Treatment Beyond Disease Progression

Accumulating evidence indicates a minority of subjects treated with immunotherapy may derive clinical benefit despite initial evidence of PD. Subjects will be permitted to continue treatment beyond site investigator assessed progression after the administration of ipilimumab for rescue as detailed in the study schema and continued nivolumab as long as they meet the following criteria:

- Site investigator-assessed clinical benefit
AND
- Subject is tolerating study drug(s).

The assessment of clinical benefit should take into account whether the subject is clinically deteriorating and unlikely to receive further benefit from continued treatment. All decisions to continue treatment beyond progression on nivolumab after addition of ipilimumab should be discussed with the sponsor-investigator and documented in the study records.

Subjects should discontinue study therapy upon evidence of further progression on nivolumab after administration of ipilimumab, defined as an additional 10% or greater increase in tumor burden volume from time of initial progression (including all target lesions and new measurable lesions).

New lesions are considered measurable at the time of progression if the longest diameter is at least 10 mm (except for pathological lymph nodes, which must have a short axis of at least 15 mm). Any new lesion considered non-measurable at the time of initial progression may become measurable and therefore included in the tumor burden measurement if the longest diameter increases to at least 10 mm (except for pathological lymph nodes, which must have an increase in short axis to at least 15 mm) on followup imaging.

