13.2.2 Definition of Secondary Endpoints

- Progression-free survival (PFS): defined as the time from nivolumab discontinuation (Arm A) or from ipilimumab initiation (Arm B) until documented progression by

RESIST criteria or death from any cause, censored at date last known progression-free for those who are alive and have not progressed.

- Overall Survival (OS): defined as the time from nivolumab discontinuation (Arm A) or from ipilimumab initiation (Arm B) until death from any cause, censored at date last known alive or at the time of last assessment of follow-up.
- Salvage therapy-free interval: defined as time from nivolumab discontinuation (arm A) to the receipt of re-starting nivolumab.
- Immune related objective response rate defined according to immune-related Responses Criteria (irRC) and detailed in section 10.5.
- Safety and tolerability according to NCI CTCAE v4.

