13.7 Efficacy Analysis

13.7.1 Primary Efficacy Analysis

Tumor assessment will be performed every 8 weeks. At the time of each restaging, subjects will be classified as achieving complete response (CR), partial response (PR), stable disease (SD), progressive disease (PD), or non-evaluable for response according to RECIST (Version 1.1) criteria.

Arm A: The proportion of subjects with sustained/continued PR or CR during the 1 year since the nivolumab discontinuation will be presented with a two-sided 90% CI using exact binominal method. Based on a sample size of 23 subjects, the confidence interval will be no wider than 0.37. For a targeted 35% PR or CR rate, the estimated PR or CR rate precision (width of two sided 90%CI) would be 0.35.

Arm B: The proportion of subjects with PR or CR during the 1-year from the date of first dose of ipilimumab will be presented with a two-sided 90% confidence interval calculated using the method of Atkinson and Brown, corresponding to the two-stage design.

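### Arm B response and PFS are timed from ipilimumab start, but no section resets the tumour reference there, so PD already present at entry can be scored as a PFS event and the shrinkage needed for PR depends on the nivolumab phase

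*Combined protocol and SAP*

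**What the plan says.** **Clock.** Section 13.7.1 takes as the Arm B primary result "The proportion of subjects with PR or CR during the 1-year from the date of first dose of ipilimumab". Section 13.2.2 runs Arm B PFS "from ipilimumab initiation (Arm B) until documented progression by" RECIST criteria, or to death.

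**Reference for response.** Section 10.3.1 defines PR as "At least a 30% decrease in the sum of the diameters of target lesions, taking as reference the baseline sum diameters". Section 10.2 adds: "The baseline sum diameters will be used as reference to further characterize any objective tumor regression in the measurable dimension of the disease". It places baseline evaluation no more than four weeks before treatment begins. It does not name nivolumab, but the only baseline imaging in the calendars is at screening, before primary nivolumab.

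**Reference for progression.** PD in 10.3.1 is a rise of at least 20% (and 5 mm) over the smallest sum on study, and "the appearance of one or more new lesions is also considered progression". Table 2 in 10.3.4 gives PD whenever a new lesion is present. The same section runs best overall response from treatment start to progression and requires confirmation.

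**Who enters Arm B.** Under 2.7, subjects enter with PD, with SD, or with a CR/PR that did not persist. Scans are every 8 weeks, "except the first imaging assessment which will take place at 12 weeks since ipilimumab addition". Section 2.7 also says: "If PD persists or develops, all treatments will be discontinued".

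**Nearest thing to a reset.** Section 10.3.2 refers to 6.7 for what counts as subsequent progression. Section 6.7 uses a rule "defined as an additional 10% or greater increase in tumor burden volume from time of initial progression", for subjects continued past progression after ipilimumab.

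**The concern.** Arm B asks what happens after ipilimumab is added to nivolumab. Its clocks start there, but the yardstick carries over from the nivolumab phase. This has three consequences.

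- A PD entrant whose disease stops growing has not progressed after ipilimumab in any ordinary sense, yet still meets the PD definition at the first Arm B scan. Arm B PFS then partly reports status at entry.
- A PD entrant with a persisting nivolumab-phase new lesion remains PD under Table 2, however far the target lesions shrink.
- An SD entrant who had nearly reached PR on nivolumab needs little further shrinkage to count as converted. A subject who regains a response that was not held would count too, although that route into Arm B is narrow.

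The Arm B rule asks for 6 responses among 57, so a few subjects scored one way or the other can change the decision. If the reference is not fixed in advance, it can be chosen after the data are seen.

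**Working it through.** **1. The plan's design figures (13.3).** Stop if 1 or fewer of 20 respond; declare active if 6 or more of 57 respond. With response rate p,

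P(active) = Σ over x = 2..20 of P[Bin(20,p) = x] × P[Bin(37,p) ≥ 6 − x].

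- p = 0.05: 4.76% (stated 4.7%); early stopping 73.6% (stated 73%).
- p = 0.20: 92.1% (stated 92%).

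The design reproduces and is not in question.

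**2. Shrinkage needed for PR, from the definitions alone.** If the entry sum is (1 + s) times baseline, the required fall from the entry scan is 1 − 0.70/(1 + s).

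| Entry change s | Required further fall |
|---|---|
| −25% | 1 − 0.70/0.75 = 6.7% |
| 0% | 30.0% |
| +20% | 1 − 0.70/1.20 = 41.7% |

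**3. Leaving PD.** An entrant at 40% over nadir must shrink by more than 1 − 1.20/1.40 = 14.3% before the target sum stops meeting the PD threshold. A persisting new lesion keeps the subject in PD whatever the sum does.

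**4. How many enter with PD.** Using historical best response as a proxy for status at entry:

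- Section 13.3 (SD 40%, PD 35%): 35/75 = 46.7%, and 57 × 0.467 = 26.6, about 27.
- Section 2.1 (SD 34%, PD 35%): 35/69 = 50.7%, and 57 × 0.507 = 28.9, about 29.

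**5. Effect on median PFS.** Let d be the PD share and f the assumed share of PD entrants no longer in PD at 12 weeks. The median falls at that scan once the share of SD entrants who have progressed reaches [0.5 − d(1 − f)]/(1 − d).

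| f (assumed) | d = 0.467 | d = 0.507 |
|---|---|---|
| 0 | 6% | none needed (d already exceeds 0.5) |
| 0.2 | 24% | 19% |
| 0.5 | 50% | 50% |

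**6. Response decision: illustrations on assumed inputs only.**

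- *Upward.* Suppose 1, 2 or 3 confirmed responders owe their PR to nivolumab-phase shrinkage and come on top of a 5% rate in the rest. The scored rate is (k + 0.05(57 − k))/57 = 6.7%, 8.3% or 10.0%, and P(active) is 11%, 22% or 39%. If such subjects are already inside the 5%, P(active) does not rise: 2.7% for one, 0.7% for two. The documents do not say which meaning the 5% has.
- *Downward.* Suppose persisting new lesions block a share b of PD entrants and true conversion is 20% in both groups. Then p = 0.20 × [0.533 + 0.467(1 − b)], which is 17.7% at b = 0.25 and 15.3% at b = 0.50. Power is 87% and 78%. With overall conversion still 20%, power is 89% and 84% if SD entrants convert at 25% and PD entrants at 14.3%. It is 85% and 71% if they convert at 15% and 25.7%.

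**The case against.** The strongest reply is that this is ordinary RECIST 1.1, which 13.2.1 names. Conversion of SD or PD to response, as 2.1 puts the question, can be read as a change of category against the original baseline. That reading is coherent, and its penalty on PD entrants is conservative for a go decision. This stands for the primary response endpoint, so the original baseline can stay. The plan should still say so for Arm B and show the nivolumab-phase contribution separately. Confirmation limits chance crossings but does not change the reference.

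A second reply is that 10.3.2 sends the reader to 6.7 for subsequent progression. Section 6.7 covers only continued treatment past progression after ipilimumab. It does not define Arm B PFS, which 13.2.2 ties to RECIST.

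A third reply is that irRC (10.5.3, 10.5.4) does not treat a new lesion in itself as progression. That does relieve the new-lesion problem, but only for a secondary endpoint, and irPR is also measured from baseline.

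Three stronger inferences are tempting and not supported:

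- *Arm B's type I error is inflated.* The two response effects oppose each other, and the result in step 6 reverses with the meaning given to the 5%.
- *Section 10.3.4 bars every PD entrant from responding.* Read literally it might, but 3.1.1, 13.7.1 and 13.7.3 plainly intend them to count.
- *The documents expressly fix a pre-nivolumab reference for Arm B.* They do not; that is the natural reading of a plan that sets no Arm B baseline.

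**Conclusion.** The point holds, and should be fixed. It is firmest for PFS: under the criteria as written, a PD entrant who is merely stable after ipilimumab is an event at 12 weeks. About 27 to 29 of 57 subjects could be exposed to this, assuming historical best response approximates status at entry. PFS is secondary and descriptive, so the harm is to interpretation rather than to a test.

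For the primary response rate, the unequal hurdles (6.7% against 41.7%) and the block from persisting new lesions follow directly from the definitions. The net direction and size of the bias do not; they depend on the SD:PD mix and on tumour changes that the documents do not give. The power and type I figures above only show that a few subjects matter under a 6-of-57 rule.

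**What to change.** These changes concern endpoint scoring only; treatment rules, sample size and the 6-of-57 rule stay as they are.

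1. State that RECIST 1.1 from the original pre-nivolumab baseline, with its new-lesion rule, drives the 6-of-57 rule, and that the 5% and 20% rates are meant on that basis. State that PD at Arm B entry does not end the response window, despite 10.3.4.
2. Add a supplementary PR/CR rate, under the same confirmation rule, with a full reset at the last pre-ipilimumab scan. Target sum, nadir and lesion list are reset together. Lesions on that scan belong to the new baseline and are never combined with the original target sum; otherwise a nivolumab-phase lesion could persist outside the sum while PR is scored.
3. Score Arm B PFS progression against the last pre-ipilimumab scan. Also report PFS with subjects who stop for PD and have no later scan counted as events at the stop, and give their number. Sections 6.6 and 8.1 describe only survival and next-therapy follow-up after stopping, so censoring these subjects may be informative. The second analysis bounds that problem but does not remove it.
4. Report response and PFS separately for SD and PD entrants.
5. Align the response window: 3.1.1 refers to the one-year point, 13.2.1 gives no window, and 13.7.1 counts responses over the year.

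The cost is wording, re-measurement of existing scans and a second tabulation, with no new patients or visits. Scored PD may differ from the PD used for treatment under 2.7. The reference scan may be old where ipilimumab is delayed (sections 6 and 6.3.2), so its age should be reported. Without a concurrent control, late nivolumab responses remain in either rate.

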10.3.2 Evaluation of Non-Target Lesions

Complete Response (CR): Disappearance of all non-target lesions and normalization of tumor marker level. All lymph nodes must be non-pathological in size (<10 mm short axis).

Non-CR/Non-PD: Persistence of one or more non-target lesion(s) and/or maintenance of tumor marker level above the normal limits.

Progressive Disease (PD): Appearance of one or more new lesions and/or *unequivocal*

progression of existing non-target lesions. *Unequivocal progression* should not normally trump target lesion status. It must be representative of overall disease status change, not a single lesion increase. For subjects who demonstrate PD at the first on-treatment imaging assessment, subjects will be allowed to remain on study until confirmatory imaging at the next imaging assessment at the discretion of the treating investigator if it appears that the subjects is clinically benefiting from treatment.

Although a clear progression of “non-target” lesions only is exceptional, the opinion of the treating physician should prevail in such circumstances, and the progression status should be confirmed at a later time by the review panel (or Principal Investigator).

For patients who continue on treatment past progression (past the confirmatory scans), see section 6.7 for details on what constitutes subsequent progression and discontinuation rules.

